This is to be filled out by RA each time a drug is requested and drawn up. Keep track of the date, the randomization id number, and whether the drug was used or thrown away.

VII: INFORMATION EXCHANGE WITH THE COORDINATING CENTER

A. Sending data collection forms

Unless otherwise arranged, each site should send completed data collection forms to the coordinating center on a weekly basis every Friday. This includes Forms 1-5 for each study patient. Study staff should ensure that all forms are complete, accurate and legible. **Original copies of all data collection forms (Forms 1-5) should be kept at the study site.** These photocopies should be kept in a secure location for 5 years.

In order to send the forms, please scan or fax the original copies of all data collection forms.

- In order to scan the forms please email them to: [contact]

B. Queries

The coordinating center will send data queries to the site study coordinators at each site as needed, with an average response time of 14 days following data collection forms being sent. These queries will be based on submitted data collection forms. Queries will be sent via email. Site study coordinators should ensure that queries are addressed appropriately and responses are sent to the coordinating center in a timely manner. Responses should be sent from the site to the coordinating center via email.

C. Sending Logs to the Coordinating Center

Study sites should send the following Logs to the coordinating center in the time frame indicated:

- Adverse Events Log: Send a copy to the coordinating center on a weekly basis. This log can be scanned/emailed ([contact]). If no adverse events have occurred during that week, site study staff should email [contact] to report that no adverse events occurred during the preceding week.

D. Protocol Updates

Protocol updates will be emailed to site investigators by the principal investigator or the site managers as they become available. A copy of each update should be printed and placed in the site's Study Binder. The coordinating center will keep a Master Protocol Updates Log of every update that is issued. A copy of this log can be requested at any time by a site as well.

E. Delegation of Authority Log

The Delegation of Authority Log provides a list of the various study tasks and responsibilities and the person(s) approved to complete these tasks. For each study responsibility, either an individual is listed by name or a category is described (RN's, midwives, residents, etc). Only someone listed by name or falling into a listed category can perform the study responsibility.

VIII. SERIOUS ADVERSE EVENTS

An adverse event is any unfavorable medical occurrence in a study participant, including any abnormal sign, symptom or disease that is temporally associated with the subject's participation in the research, whether or not it is considered related to the subject's participation in the research.

A serious adverse event (SAE) is an event that:

- Is life threatening
- Requires inpatient hospitalization or prolongation of existing hospitalization
- Results in a permanent or serious disability
- Results in a congenital abnormality
- Results in death

Important medical events that may not result in death, be immediately life-threatening, or require hospitalization may be considered an SAE when, based upon appropriate medical judgment, they may jeopardize the subject and may require medical or surgical intervention to prevent one of the outcomes listed in this definition. Examples of such events are intensive treatment in an Emergency Room or at home for allergic bronchospasm; blood dyscrasias, or convulsions that do not result in hospitalization; or development of drug dependency or drug abuse.

Reporting SAEs

All SAEs, whether or not there is a probable relationship with the study drug or with the study procedures, must be reported by the site investigator to their coordinating center site manager within 24hrs of his/her becoming aware of the SAE. Coordinating center staff will report SAEs promptly to NEIRB and the IDMC. Sites using their own IRB must additionally report the SAE to their IRB (FPAWH in Long Beach and Los Angeles should report any SAE's to the Coordinating center. Lovejoy clinic should report any SAE's to both the Coordinating Center and their own IRB). Site investigators must also report all SAEs occurring up to two weeks after the participant is discharged from the study IF the event is thought to be related or possibly/probably related to the study.

Reporting of a SAE can be done by phone or email. When reporting a SAE to the coordinating center, the site investigator should refer to the subject by her Enrollment ID to protect patient privacy. Sites will work with the coordinating center to complete the Serious Adverse Event Reporting Form after this initial contact is made to report the SAE.

Principal investigator: [name], MPH. [contact]
[contact]

Research manager:

[name]
[contact]
[contact]

Assessing AEs

Monitoring for and documentation of adverse events related to the cervical dilation, medication injection and/or D&E of study participants, whether anticipated or unanticipated, is the responsibility of the site investigator, who will maintain oversight of the site's adverse events, but she may delegate collection of information related to this function to the site's research coordinator.

Possible adverse events related to the medication injection include those below.

- Injection site pain or bruising
- Nausea and vomiting
 - o Only report in AE log if patient reports severe nausea or vomiting, patient treated with more than one anti-emetic agent (ex. Zofran and Compazine), or patient treated with multiple doses of anti-emetic agent (ex. Patient given 3 doses of Zofran for nausea).
- Out of hospital delivery
- Bradycardia
- Endometritis, sepsis

Possible adverse events related to the D&E include those below. None of the risks listed below would be solely due to the study procedures but are rather potential adverse events that may be related to standard D&E or anesthesia/analgesia/uterotonic agents that accompany the D&E.

- Hemorrhage
 - o Requiring intrauterine tamponade (with Foley, Bakri, packing)
 - o Requiring transfusion
 - o Requiring embolization
- Uterine re-evacuation (for retained tissue, hematometra, bleeding)
- Endometritis, sepsis
- Cervical laceration requiring stitches
- Uterine perforation
- Abdominal surgery (laparoscopy, laparotomy, hysterectomy)

- Transfer to the hospital for any indication (even if the subject is not admitted)
- Allergic reaction/hypersensitivity/anaphylactic shock
- Vasovagal episode
- Syncope
- Anesthesia complications
- Cardiopulmonary arrest

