 - a. NOTE: anxiety that is listed in the chart as a chronic condition (i.e. has been diagnosed by a healthcare professional and/or uses medication to manage) then this should be considered "psychiatric disease". If the chart notes that the patient is generally feeling anxious (for example, is feeling anxious about the abortion procedure), this does not need to be noted.

This is the end of **Form 1: Eligibility Screening and Baseline Data, Day 1.**

Upon completion of Form 1, study staff should:

- Review Form 1 for accuracy and completeness
- Make corrections as necessary. Date and initial all corrections.
- Sign both sides of the Form in the header (next to "Staff signature")
- Once clinician/physician has completed H&P with patient, confirm eligibility criteria with clinician/physician and have physician sign Form 1 under "Clinician signature)
- Proceed to Randomization, Drug Tracking Log, Drug Drawing**
- When patient is taken to room for dilator placement and injection, proceed to **Form 2: Dilator and Injection Data, Day 1**

B. Form 2: Dilator and Injection Data, Day 1

Form 2 Overview

Form 2 is used to document the injection of the study medication and dilator placement. It also assesses the pain felt by the patient during the dilator placement and injection. This form will be completed by IRB-approved study staff before and after the injection and during dilator placement. The staff member will survey both the provider and the participant while completing.

Injection and dilator order will vary by site. LOVEJOY: Injection will happen first, followed by dilator placement. FPAWH: Dilators will be placed first, followed by injection. SFGH: Order may vary.

The Injection Questionnaire and the Dilators Questionnaire should be asked and answered about the specific event to which they refer (injection or dilator placement). Please perform the questionnaires DIRECTLY after each event and clarify for the participant that the questions are referring to that event only.

Form 2 Detailed Instructions

Injection data on Form 2:

Write the participants Randomization ID in the box provided. The randomization ID contains the group assignment code 1 or 2 followed by the site specifier (1 for SF, 2 for LJ, 3 for LA, 4 for LB) and the patient-specific number (01, 02, 03). For example, a Group 1 participant from SF would have the Randomization ID 1-101.

Summary of Randomization IDs:

- First number = GA group (1= BPD 4.61-5.24cm, 2= BPD 5.25-5.88cm)
- Dash

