5. Record the time that the injection was completed and circle "AM" or "PM". Record the time as standard time (12hr format), hh:mm. No stopwatch is needed. Injection is considered complete when all study medication has been administered.

Directly after the injection procedure is complete, ask the patient items 6-9.

6. Ask the patient to assess her pain specifically during her injection on a scale of 0-10. Show her the 0-10 scale on Form 2 and read the question as printed on the Form. Ask her to select the appropriate box on the scale. Mark an "X" in the appropriate box, based on her response.
7. Ask the patient how acceptable this amount of pain was to her. Read the 5 response choices to the patient: "Very acceptable", "Somewhat Acceptable", "Somewhat Unacceptable", or "Very Unacceptable". Tick the appropriate response. If the patient is unable to answer the question, tick "Don't know".
8. Ask the patient how the injection compared to her expectations prior to the procedure. Read her the 3 answer choices "Better than expected", "The same as expected", "Worse than expected" and tick the appropriate response. If the patient is unable to answer the question, tick "Don't know".
9. Ask the patient if she is experiencing any nausea right now. If she is not experiencing nausea currently, circle "None" on the corresponding line. If she is experiencing nausea, ask her if it was mild, moderate, or severe and circle her response. If the woman would like the study staff to define mild, moderate or severe, read her the definitions below. These definitions are also printed directly on Form 2:

Mild: Symptoms were annoying but did not get in the way of your usual activities.

Moderate: Symptoms got in the way as you tried to do your usual activities but you were still able to do most of the things you needed to.

Severe: Symptoms stopped you from being able to do your usual activities.

Osmotic dilator placement occurring during Form 2

Osmotic dilators should only be placed by clinicians specified in the Delegation of Authority Log.

Items 10-16 should be recorded by study staff during the dilator placement.

10. Record whether the dilators were placed in the patient's cervix prior to her study drug injection or after by checking "Before" and "After"
11. Record the number of Laminaria dilators and the number of Dilapan dilators successfully placed in the cervix.

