- The next data collection form to be completed will be **Form 3: Arrival Data, Day 2**. Form 3 must be completed when the patient arrives at the clinic on Day 2.

C. Form 3: Arrival Data, Day 2

Form 3 Overview

Form 3 is used to assess the patient's experience of any side effects or adverse events since she was last seen in the clinic on Day 1. Form 3 will also document any pain the patient is having currently. Form 3 should be completed when the patient arrives to clinic on Day 2.

Form 3 Detailed Instructions

1. Record today's date. Dates should be recorded as month/day/year (MM/DD/YYYY).
2. Take the patient's temperature as soon as possible after she arrives in the clinic. Record the patient's temperature in degrees Fahrenheit.
3. Ask the patient if she has experienced the following symptoms since she left clinic yesterday: Nausea, vomiting, chills, fever, dizziness. If she did not experience the symptom, circle "None" on the corresponding line. If she did experience the symptom, ask her if it was mild, moderate, or severe and circle her response. If the woman would like study staff to define mild, moderate, or severe, read her the definitions below. These definitions are also printed directly onto Form 3:

Mild: Symptoms were annoying but did not get in the way of your usual activities.

Moderate: Symptoms got in the way as you tried to do your usual activities but you were still able to do most of the things you needed to.

Severe: Symptoms stopped you from being able to do your usual activities.

4. Ask the patient if they took any narcotics for pain since leaving the clinic yesterday. If they need further examples, read the examples listed "Norco, tyco or T3, Percocet, Vicodin". If they have taken a narcotic since leaving the clinic yesterday, check "Yes" and print the medication name. If they haven't taken any narcotics, check "No".
5. Ask the patient if they took any other medication for pain since leaving the clinic yesterday. If they need further examples, read the examples listed

- “ibuprofen, tylenol”. If they have taken any other medications for pain since leaving the clinic yesterday, check “Yes” and print the medication name. If they haven’t taken any other medications, check “No”.

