6. Ask the patient if they took any medication for nausea since leaving the clinic yesterday. If they have taken any medications for nausea since leaving the clinic yesterday, check “Yes” and print the medication name. If they haven’t taken any other medications, check “No”.
 7. Ask the patient if they called the clinic for any reason since leaving the clinic yesterday. If they have called the clinic check “Yes” and print the reason for their call. If they haven’t taken any other medications, check “No”.
 8. Ask the patient if they went to an Emergency Room or any other clinic for any reason since leaving the clinic yesterday. If they did go to an Emergency Room or another clinic check “Yes” and print the reason for their visit. If they haven’t taken any other medications, check “No”.
 9. Ask the patient what their bleeding has been like since leaving the clinic yesterday. Read them the question as printed followed by the following 4 responses: “No bleeding”, “Spotting or light bleeding only”, “Moderate bleeding (like a period)”, or “Heavy bleeding (heavier than a bleeding)”. Tick the appropriate response.
 10. Ask the patient if they noticed the fetus had stopped moving?. If they say yes, check “Yes” and record the approximate time they last felt fetal movement if they can remember. Record the time in 12hr format, as hh:mm and circle AM or PM. If they don’t remember, write “99:99”. If they have not felt any stop in fetal movement, check “No”.
 11. Ask the patient which medication they think they received yesterday. Check the appropriate response and write why they think they received that particular medication. If the participant cannot offer a guess of which medication she received check “Don’t Know”.
 12. Ask the patient to assess her pain currently on a scale of 0-10. Show her the 0-10 scale on Form 3 and read the question as printed on the Form. Ask her to select the appropriate box on the scale. Mark an “X” in the appropriate box, based on her response.
 13. Ask the patient how acceptable this amount of pain was to her. Read the 5 response choices to the patient: “Very acceptable”, “Somewhat

Acceptable", "Somewhat Unacceptable", or "Very Unacceptable". Tick the appropriate response. If the patient is unable to answer the question, tick "Don't know".

14. After the patient questionnaire is completed, refer to the patient's medical chart. Check "yes" or "no" to reflect whether misoprostol was given adjunctively.

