3. Ask the patient how acceptable this amount of pain was to her. Read the 5 response choices to the patient: "Very acceptable", "Somewhat Acceptable", "Somewhat Unacceptable", or "Very Unacceptable". Tick the appropriate response. If the patient is unable to answer the question, tick "Don't know".
4. Ask the patient if she has experienced the following symptoms since she left clinic yesterday: Nausea, vomiting, chills, fever, dizziness. If she did not experience the symptom, circle "None" on the corresponding line. If she did experience the symptom, ask her if it was mild, moderate, or severe and circle her response. If the woman would like study staff to define mild, moderate, or severe, read her the definitions below. These definitions are also printed directly onto Form 5:

Mild: Symptoms were annoying but did not get in the way of your usual activities.

Moderate: Symptoms got in the way as you tried to do your usual activities but you were still able to do most of the things you needed to.

Severe: Symptoms stopped you from being able to do your usual activities.

5. Ask the patient how satisfied they are with their abortion procedure overall. Read the choices "Very satisfied", "Somewhat satisfied", ,

“Somewhat unsatisfied” and “Very unsatisfied”. Record their response by checking the appropriate box.

6. Ask the patient how satisfied they are with specifically their injection procedure overall. Read the choices “Very satisfied”, “Somewhat satisfied”, “Somewhat unsatisfied” and “Very unsatisfied”. Record their response by checking the appropriate box.
7. Ask the patient if she were to become pregnant in the future and need a second trimester abortion similar to her procedure today, would she prefer to get the digoxin injection or not have the injection. Record whether she would rather have the injection, not have the injection or not sure by checking the appropriate box. Record the reason for her response on the line provided.
8. Ask the patient if they would recommend the digoxin injection to other women having a second trimester abortion. Record whether she would recommend having the injection or not having the injection, or whether she is not sure, by checking the appropriate box. Record the reason for her response on the line provided.

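### Apart from one nausea question, no form asks about the Day 2 symptom list for the time between the injection and leaving the clinic on Day 1

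*Combined protocol and SAP*

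**What the plan says.** Form 3 (section V.C) is meant to "assess the patient's experience of any side effects or adverse events since she was last seen in the clinic on Day 1". Item 3 carries this out with the instruction "Ask the patient if she has experienced the following symptoms since she left clinic yesterday: Nausea, vomiting, chills, fever, dizziness", each symptom graded from none to severe. The medication items that follow use the same start point; item 6, for example, reads "Ask the patient if they took any medication for nausea since leaving the clinic yesterday".

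Form 5 (section V.E), completed after the procedure, repeats the stem in item 4: "Ask the patient if she has experienced the following symptoms since she left clinic yesterday".

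Form 2 (section V.B) is the only form completed between the injection and departure. Its instruction is "Directly after the injection procedure is complete, ask the patient items 6-9". Items 6 to 8 concern pain and expectations of the injection. Item 9 is the one question on a symptom from the Form 3 list: "Ask the patient if she is experiencing any nausea right now".

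Section VIII (Assessing AEs) names nausea and vomiting as possible effects of the injection, with a restriction: "Only report in AE log if patient reports severe nausea or vomiting", or if more than one anti-emetic agent or several doses were given. The same section sends Day 1 adverse events to Form 2 and the Adverse Event Log.

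The order of procedures differs by site (Form 2 Overview): "LOVEJOY: Injection will happen first, followed by dilator placement". At the two FPAWH sites dilators come first, and at SFGH the order varies.

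**The concern.** Exposure begins at the injection, but the solicited symptom window begins when the woman walks out. What lies between is the earliest part of exposure to a drug whose listed possible effects include nausea and vomiting. An episode that comes and goes while she is still in the clinic can be missed by a questionnaire written to collect side effects.

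What is at stake is how completely the trial can describe early tolerability in each arm. Departure time on Day 1 is not recorded, so the length of the uncovered interval cannot be established from the data afterwards.

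**Working it through.** No figure in the plan bears on this point, so the check sets the items side by side.

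**Symptoms, by the period each item covers**

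| Symptom | Before injection (Form 1) | Directly after injection (Form 2) | From then until leaving | After leaving (Form 3 item 3, Form 5 item 4) |
|---|---|---|---|---|
| Nausea | Now, and past week (items 25, 26) | Now (item 9) | Not asked | Asked |
| Vomiting | Past week (item 27) | Not asked | Not asked | Asked |
| Fever | Only as an eligibility exclusion (item 10) | Not asked | Not asked | Asked |
| Chills, dizziness | Not asked | Not asked | Not asked | Asked |

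**Which episodes are lost**

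1. Present when item 9 is asked, nausea only: captured on Form 2.
2. Begins in clinic and is still present on leaving, any of the five: captured on Form 3, because she has the symptom after departure.
3. Vomiting, chills, fever or dizziness that begins and ends between injection and leaving: solicited nowhere.
4. Nausea that begins after item 9 and ends before leaving: solicited nowhere.

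The gap consists of cases 3 and 4 only.

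**Treatment, by the period each item covers**

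- Form 2 item 2: pain medication given before the injection and dilators.
- Form 3 items 4 to 6: pain and nausea medication from leaving onwards.
- Form 3 item 15: other medication given after arrival on Day 2.

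An anti-emetic given in the clinic after the injection on Day 1 falls under none of these. The Adverse Event Log has a treatment field, but only for an event that is logged.

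**The unsolicited route**

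- Section VI.D defines an adverse event broadly, over the whole study. Section VIII directs Day 1 events to Form 2 and the log.
- The item-by-item instructions for Form 2 (items 1 to 19) contain no general adverse event item.
- For nausea and vomiting, the log threshold leaves out a mild or moderate episode treated with no more than one dose of one agent.
- Chills, fever and dizziness have no such threshold, but depend on someone volunteering or noticing them.

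**Length of the gap**

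Form 2 item 5 records when the injection ended and item 12 when dilator placement ended. Where injection comes first, the difference gives a lower bound on the gap. No item gives the upper end: Form 5 item 10 records discharge on Day 2 only.

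For scale, assume a gap g of 0.25 to 2 hours and set it against the planned injection-to-procedure interval T of 16 to 24 hours given in the opening section. The share of time is g / T:

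- g = 0.25 h: 0.25/24 = 1.0% to 0.25/16 = 1.6%
- g = 1 h: 1/24 = 4.2% to 1/16 = 6.25%
- g = 2 h: 2/24 = 8.3% to 2/16 = 12.5%

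The values of g are assumptions. The result is a share of time, not of events. Turning it into a number of missed events would need onset data, which the documents do not give.

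**The case against.** The strongest reply has four parts.

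- **The start point fits the form's purpose.** Form 3 is described as covering the time since the woman was last seen, and leaving the clinic is a clear anchor that is the same at every site. This is true, but Form 2 does not then cover the time before it, so the two forms do not join up.
- **The woman is with staff during the gap.** Anything notable should be seen and entered as a Day 1 adverse event; vasovagal episode, syncope and bradycardia are listed by name. This stands for notable events. It leaves brief, mild or moderate symptoms, which a graded questionnaire is there to collect.
- **Symptoms are not an endpoint.** Section IX names operative time as primary, and ease of procedure, fetal demise and complications as secondary. This stands, and it limits the consequence to describing tolerability.
- **Moving the window has its own cost.** It would take in dilator placement where injection comes first and not where it comes last. This also stands and is dealt with in the remedy.

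A reader might also infer more than the text supports:

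- *That no post-injection symptom is solicited on Day 1.* Form 2 item 9 asks about nausea, with a matching baseline in Form 1 item 25.
- *That digoxin effects are undercounted, or that the drug will look better tolerated than it is.* There are no onset data, the gap applies to both arms, and symptoms that outlast departure are captured.
- *That a stated amount of power is lost.* No symptom comparison is powered, and any such figure would rest on invented rates and missed fractions.
- *That the gap is short at FPAWH because injection comes last.* Time from the last procedure to departure is not given for any site.
- *That site differences bias the comparison of arms.* Randomization numbers run separately by site and gestational-age group, so both arms at a site share the same practice.

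**Conclusion.** The concern holds in a limited form. The windows leave an interval, from just after the injection to departure on Day 1, in which none of the five listed symptoms is solicited. Within it, only symptoms that begin and end there are lost, and only if they also escape unsolicited reporting. Early, short-lived side effects may therefore be under-ascertained in both arms.

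The size cannot be calculated from the documents. The conclusion rests on the item instructions in the SOP being a full account of what the forms ask. It does not depend on any assumed symptom rate or length of stay. It is a worthwhile, inexpensive improvement to safety ascertainment and not a threat to the trial's main result.

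**What to change.** 1. Change the stem of Form 3 item 3 to ask about symptoms *since your injection yesterday*. The start time is already recorded in Form 2 item 5.
2. Use the same start point in Form 3 items 4 to 6, so that pain and nausea medication given in the clinic after the injection is covered as far as the woman can recall it.
3. Reconcile the stem of Form 5 item 4, so that the two symptom windows are consistent and do not differ by accident.
4. Keep Form 2 item 9 as the immediate reading. It will overlap the new window, so report the two separately and do not add them.
5. State in section IX that symptom rates are compared between arms within site and not across sites.

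The cost is a wording change to two forms and the SOP, with no extra visit, staff or question. The downside is that the new window includes dilator placement at Lovejoy and sometimes at SFGH, but not at FPAWH. Both arms within a site share this equally, and Form 2 item 10 already records the order.
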